## **Overall Survival**

OS is calculated as the time from the first dose of AMG 562 until death due to any cause. Subjects who are alive at the date that triggers the analysis will be censored at the date last known to be alive. If the date last known to be alive is after the date that triggers the analysis, the subject will be censored at the analysis trigger date.

Last known alive date: For subjects who do not have death date available i.e. subject was alive throughout, last known alive date is defined as the latest of all the date variable in the study.

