## 8.3 Handling of Missing and Incomplete Data

Incomplete adverse event and concomitant medication dates missing data will be imputed as described in Appendix A. For efficacy data of overall response, subjects without tumor response assessments will be considered as non-responders. Otherwise, only nonmissing data will be analyzed.

Ineligible subjects and subjects enrolled in Part 1 who are not DLT evaluable may be replaced.

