## 14. Appendices

## Appendix A. Imputation Rules for Partial or Missing Stop Dates

If the month and year are present, impute the last day of the month. If only the year is present, impute December 31 of that year. If the stop date is entirely missing, assume the event or medication is ongoing. If a partial or complete stop date is present and the 'ongoing' or 'continuing' box is checked, then it will be assumed that the AE or concomitant medication stopped and the stop date will be imputed, if partial.

	Stop Date								
		Complete: yyyymmdd		Partial: yyyymm		Partial: yyyy			
Start Date		< 1 st Dose	≥ 1 st Dose	< 1 st Dose yyyymm	≥ 1 st Dose yyyymm	< 1 st Dose уууу	≥ 1 st Dose уууу	Missing	
Partial: yyyymm	rtial: = 1 st Dose yymm yyyymm	- 2	1	- 2	1	N/A	1	1	
	≠ 1 st Dose yyyymm		2		2	2	2	2	
Partial: yyyy	= 1 st Dose уууу	- 3	1	. 3	1	N/A	1	1	
	≠ 1 st Dose уууу		3		3	3	3	3	
Missing		4	1	4	1	4	1	1	

Imputation Rules for Partial or Missing Start Dates

1 = Impute the date of first dose

2 = Impute the first of the month

3 = Impute January 1 of the year

4 = Impute January 1 of the stop year

Note: For subjects who were never treated (first dose date is missing), partial start dates will be set to the first day of the partial month.

Note: If the start date imputation leads to a start date that is after the stop date, then do not impute the start date.

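### The overall survival censoring date is the latest of every date in the study, with no exclusion of imputed or non-contact dates, so a lost subject can be credited with survival time that was not observed.

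*SAP*

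**What the plan says.** The OS definition in SAP Section 5 sets the censoring rule: "Subjects who are alive at the date that triggers the analysis will be censored at the date last known to be alive". It limits that date in one way only: "If the date last known to be alive is after the date that triggers the analysis, the subject will be censored at the analysis trigger". It then defines the date itself. The definition opens "For subjects who do not have death date available i.e. subject was alive throughout", and continues that "last known alive date is defined as the latest of all the date variable in the study".

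SAP Section 8.3 adds: "Incomplete adverse event and concomitant medication dates missing data will be imputed as described in Appendix A". Appendix A gives the rules for stop dates:

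- Month known: "If the month and year are present, impute the last day of the month".
- Year only: "If only the year is present, impute December 31 of that year".
- Nothing known: "If the stop date is entirely missing, assume the event or medication is ongoing".

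Protocol Section 10.5.3.2 has the same OS censoring rule but does not define the date last known alive, so it does not narrow the SAP wording. SAP Section 9.5.2 keeps Kaplan-Meier estimation of OS, with Brookmeyer-Crowley 90% intervals, among the outputs of the discontinued study.

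**The concern.** A last-known-alive date should rest on evidence that the subject was alive on that day. Here the rule is a maximum over all dates, and a maximum favours whichever dates have been shifted late. Appendix A shifts partial stop dates to the end of the period they name, and it does not truncate them at the subject's last contact. The words about all date variables also take in, on their face, dates that record no contact with the subject. The definition further treats the absence of a death date as proof of being alive, so it covers subjects whose vital status is simply unknown.

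The SAP is more careful with its other time-to-event endpoints. PFS is censored at the last PET-CT assessment, and the added censoring rule for duration of response uses the last evaluable PET-CT scan. OS alone has an open-ended source.

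What is at stake is the OS curve. A subject kept in the risk set past the last date known alive enlarges the denominator at later deaths. In a study stopped early, a few such subjects could move the tail.

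**Working it through.** The documents give no OS event count, OS rate or number of subjects lost, so there is no figure of the plan to reproduce. The check compares the rules with one another and bounds the overshoot.

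**1. Overshoot from one imputed stop date.** Let I be the imputed stop date, L the latest observed date showing the subject alive, and T the analysis trigger date, with L on or before T. Then

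overshoot = max(0, min(I, T) − L).

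**2. Largest values.** The partial date itself is taken to show the subject alive on the first day of the period it names.

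| Stop date known to | Imputed as | Largest overshoot |
|---|---|---|
| Month | Last day of month | 31 − 1 = 30 days |
| Year | December 31 | 365 − 1 = 364 days (365 in a leap year) |
| Not at all | Ongoing, no date created | 0 days |

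If a genuine contact falls on or after I, then L ≥ I and the overshoot is zero.

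**3. What the cap does.** Assume a last contact on 15 March 2020 and a stop date known only as 2020, so that I is 31 December 2020.

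- T = 30 June 2020: overshoot = 30 June − 15 March = 107 days.
- T = 31 December 2020 or later: overshoot = 31 December − 15 March = 291 days.

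The cap shortens the overshoot when the trigger falls before I. It does nothing when the trigger falls later. Under SAP Sections 7.2 and 7.3 the primary analysis is at the termination decision and the final analysis waits for the last patient to end the study. A subject lost well before either can be carried forward without the cap binding.

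**4. Direction of the effect.** The following data are invented, to show direction only: 10 subjects; deaths at months 2, 5, 7, 9 and 11; three censored at months 14, 15 and 16; two lost at months 3 and 4.

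- Censored at true last contact: 12-month OS = 9/10 × 6/7 × 5/6 × 4/5 × 3/4 = 0.386.
- The two lost subjects carried to months 12 and 12.9: 12-month OS = 9/10 × 8/9 × 7/8 × 6/7 × 5/6 = 0.500.

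Later censoring can only enlarge risk sets, so each Kaplan-Meier factor stays the same or rises. If no death falls in the added interval, the estimate does not change.

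**The case against.** The strongest reply is that the SAP never says imputed dates feed this derivation. Section 8.3 introduces imputation for adverse events and medications and does not link it to OS, and no list of date variables is given. A programmer might well use only raw contact dates. That stands as far as it goes: a reader might infer that lost subjects will receive unobserved time, and the documents support only that they can. The part about non-contact dates rests wholly on the literal breadth of the definition.

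A reader might also take the mean gap to the imputed date as the typical effect: 364/2 = 182 days for a year-only date and about 15 for a month-only date. That is not what the rule adds, because it takes a maximum over later real contacts and is capped at the trigger. If, for example, the stop date and last contact are the earlier and later of two uniform dates in the same year, the mean overshoot before the cap is 365/3, about 122 days. With a month-only date and both in the same month it is about 10 days. No average can be claimed from the documents.

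Follow-up limits exposure further:

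- General concomitant medication is collected only to the safety follow-up visit (Protocol Section 7.3.5).
- Non-serious adverse events are collected over the same period (Section 9.2.2.1).
- Survival is followed every 3 months after progression, with public databases allowed, up to 2 years from first dose (Section 7.2.4).
- Vital status is required for all subjects within local law (Section 7.3.14).

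A genuine later contact will therefore often overtake a partial stop date. SAP Section 7.2 also expects data up to long-term follow-up for all but one ongoing subject.

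These facts reduce how often the problem can arise. They do not change the rule: a subject lost around safety follow-up with a partial stop date is still exposed. Anti-lymphoma therapy also continues to be recorded after that visit.

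**Conclusion.** The point holds as a defect of definition. The SAP states a positive rule that is too broad, and followed literally it can censor a subject after the last date known alive and bias the OS curve upward. The bound per affected subject is 30 days (month-only) or 364 to 365 days (year-only), before the cap and any later contact reduce it. This assumes that imputed dates are allowed into the maximum, which the SAP does not exclude.

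The documents do not show that any subject is lost, has a partial stop date, or is affected, so the effect on the reported OS cannot be sized. The shift from 0.386 to 0.500 must not be read as an estimate for this trial. OS is a secondary endpoint, SAP Section 2.2 makes all analyses descriptive, and the stated futility and DLT stopping rules do not use OS. It is a minor correction, worth making because the censoring date should be reproducible.

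**What to change.** Replace the last-known-alive sentence in the SAP's OS definition with a rule of this kind: the latest observed, non-imputed date that shows the subject was alive, taken from visits, assessments, dosing, sample collection, adverse event start, survival follow-up contact, or public-record confirmation of vital status (which Protocol Sections 7.2.4 and 7.3.14 allow). State that imputed dates and administrative dates, such as data entry, laboratory processing and sponsor decisions, are excluded. Keep the cap at the analysis trigger date.

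The cost is one SAP sentence and the matching line in the derivation specification. No new data are needed.

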## **Progression Free Survival (PFS)**

PFS is calculated as the time from the date of first dose of AMG 562 until the date of diagnosis of progression of lymphoma, or date of death, whichever is earliest. Subjects who are alive and did not have progression will be censored at the last date of radiographic assessment of PET-CT scans.

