f ECGs and vitals should be performed prior to any invasive procedures. ECGs are only required in treatment cycle 1 and 2. In case of intra-subject dose escalation: conduct ECGs as in cycle 1 during the first cycle after dose escalation. Starting with cycle 3, time points for vital sign measurement > 4 h after each infusions apply if the subject is still hospitalized at the time.

g For premedication details see Section 6.3

h Serum pregnancy test required at screening. For later time points, urine pregnancy test is allowed. In case of a positive result, serum pregnancy test should be repeated. Pregnancy tests will be performed for all females unless surgically sterile or > 2 years postmenopausal.

Ferritin assessment to be performed at onset of CRS, and daily until values are back to baseline/event is resolved.

j Predose anti-AMG 562 antibody sample in every 2nd cycle after cycle 1 (C1D1, C1D15 C3D1, C5D1, ..).

q PET/CT will be performed at screening, week 5, week 15, week 25, and at end of treatment if end of treatment is at week 35 or beyond. Clinical tumor assessments will be performed at screening, week 5, week 15, week 25, and at end of treatment if end of treatment is at week 35 or beyond. Every attempt should be made to complete PET and CT within 3 days of each other, particularly during treatment. If subject discontinues study treatment for any reason, including toxicity or clinical evidence of disease progression, PET/CT should be conducted 14 (+ 3) days following the last dose of AMG 562.

r In case of seizure of any grade perform brain MRI and cerebro spinal fluid (CSF) analysis, if there are no contraindications.

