### 7.2.2 Treatment

The following procedures will be completed during the treatment period at the times designated in the Schedule of Assessments (Table 5 through Table 8).

Subjects will be hospitalized as outlined in Section 6.2.1.1.

Treatment begins on Day 1 when the first investigational product infusion is administered to a subject.

Prior to each start of investigational product infusion all protocol-required predose assessments including premedication have to be performed.

Results of any predose laboratory tests will not have to be available before starting the infusion with AMG 562. Laboratory assessments that were done within 24 hours prior to infusion start do not need to be repeated prior to infusion.

The following procedures will be completed during the treatment period at the times designated in the Schedules of Assessments (Table 5 through Table 8):

- hospitalization
- physical examination
- ECOG performance status
- weight
- vital signs (ie, blood pressure, heart rate, respiratory rate, temperature)
- pulse oximetry
- ECG triplicate measurement
- laboratory assessments: hematology, chemistry, coagulation, urinalysis, urine/serum pregnancy test (females only and not required if surgically sterile or ≥ 2 years postmenopausal), ferritin, immunoglobulins, anti-AMG 562 antibody sample collection
- AMG 562 PK sample collection
- •
- serious adverse event reporting
- disease assessments:
  - for all subjects: Clinical tumor and radiographic assessment (PET/CT) at week 5, week 15, week 25, and at end of treatment if end of treatment is at week 35 or beyond

- adverse event reporting
- disease-related event reporting
- documentation of concomitant medication
- administration of protocol-required therapies
- For subjects to whom intra-subject dose escalation applies:
- Subjects should be hospitalized as outlined in schedule of assessment section 7.1. Hospitalization may also be required at other times (eg, intra-subject dose escalation).
- All other assessments should be performed as per the schedule of assessments applicable to the actual cycle

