# 7.2.4 Long-term Follow-up

Following the SFU visit, there will be a LTFU period for clinical evaluation of disease status and survival. Subjects will be followed via on-site visit every 6 weeks ( $\pm$  3 days) for assessments of disease status and documentation of anti-lymphoma treatment until progression of disease. From this time point onwards subjects will be followed every 3 months ( $\pm$  2 weeks) for survival and anti- lymphoma treatment (on-site visits are not required, if needed also interrogation of public databases is acceptable). Subjects will be followed for a maximum of 2 years from the first dose of AMG 562, or until subject death, whichever occurs first.

Subjects will allow Amgen continued access to medical records so that information related to subjects' health condition, including disease status and survival, may be obtained.

The following procedures will be performed during the LTFU as designated in the Schedules of Assessments (Table 8) as long as on-site visits apply.

- laboratory assessments: immunoglobulins
- disease assessments
- serious adverse event reporting (see Sections 9.2.2.2 and 9.2.2.3 for reporting requirements during the LTFU period)

perform assessments driven by observation of CR/progression/relapse, or CRS as listed in Section 7.2.2.

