#### QTcF=QT/(RR/1000)1/3

## Long Term Follow Up (LTFU)

Following the SFU visit, there will be a LTFU period for clinical evaluation of disease status and survival. Subjects will be followed via on-site visit every 6 weeks (± 3 days) for assessments of disease status and documentation of anti-lymphoma treatment until progression of disease. From this time point onwards subjects will be followed every 3 months (± 2 weeks) for survival and anti- lymphoma treatment (on-site visits are not required, if needed also interrogation of public databases is acceptable). Subjects will be followed for a maximum of 2 years from the first dose of AMG 562, or until subject death, whichever occurs first.

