9.5.2 Analyses of Secondary Efficacy Endpoint(s)

Subject listings will be provided based on the available efficacy data.

Proportion of subjects with best overall response and by best overall response category will be presented. Response will be determined by Lugano classification

which includes complete metabolic response (CMR), partial metabolic response (PMR), no metabolic response (NMR) and progressive metabolic disease (PMD).

Proportion of subjects with an objective response of CMR or PMR per Lugano classification along with corresponding 90% CI will be calculated using Clopper-Pearson method.

DOR will be calculated only for subjects who achieve a best overall response of PMR or better. Subjects will be censored following the censoring strategy described in the definition of DOR. The distribution of DOR, including the median and quartiles will be characterized using the Kaplan-Meier(KM) method based on the subjects who achieve a best response of PMR or better. The 90% CIs for the median and quartiles of DOR will be constructed using the Brookmeyer and Crowley method.

The distribution of PFS, including median, will be estimated using the Kaplan-Meier method. The 90% CIs for the median and other percentiles of PFS will be constructed using the Brookmeyer and Crowley method.

OS will be analyzed using the same method as describe for the PFS endpoints.

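### PFS counts progression or death at any time but credits event-free follow-up only to the last PET-CT, which tends to lower late PFS unless long-term follow-up includes PET-CT; DOR has two conflicting censoring dates

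*SAP*

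**What the plan says.** **PFS.** SAP Section 5 runs PFS from first dose "until the date of diagnosis of progression of lymphoma, or date of death, whichever is earliest", with no limit tied to the last scan. Subjects without an event are handled differently: "Subjects who are alive and did not have progression will be censored at the last date of radiographic assessment of PET-CT scans". Protocol 10.5.3.2 has the same rule. SAP 9.5.2 reports "The 90% CIs for the median and other percentiles of PFS".

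**Scans.** The PET/CT footnote to Table 11 (Protocol 7.1) reads "PET/CT will be performed at screening, week 5, week 15, week 25, and at end of treatment", the last of these only if treatment ends at week 35 or beyond. After discontinuation for any reason, "PET/CT should be conducted 14 (+ 3) days following the last dose of AMG 562". It lists no LTFU scan.

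**LTFU.** SAP Section 5 and Protocol 7.2.4 require on-site visits every 6 weeks "for assessments of disease status and documentation of anti-lymphoma treatment until progression of disease", up to 2 years from first dose. Protocol 7.2.4 adds "The following procedures will be performed during the LTFU as designated in the Schedules of Assessments (Table 8) as long as on-site visits apply", and the list that follows includes disease assessments without naming the modality. In Protocol 7.2.2 the same term is spelled out as "Clinical tumor and radiographic assessment (PET/CT) at week 5, week 15, week 25" and at a late end of treatment. Protocol 3.1 and SAP 3.1 mention only 3-monthly survival follow-up once response evaluations stop.

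**DOR.** SAP Section 5 first censors at the last disease assessment, capped at the analysis trigger date. A closing sentence then censors at the last evaluable PET-CT. Protocol 10.5.3.2 has only the first rule.

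**The concern.** Kaplan-Meier needs the same follow-up clock for subjects with and without events. Here a subject who progresses or dies in LTFU stays in the risk set until that date. A subject seen at the same visits and found clear is removed at the last PET-CT, which may be about two weeks after the last dose. The late risk set is then enriched for subjects who go on to fail, and the curve is pulled down.

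The subjects most affected stop treatment while progression-free. The Protocol Synopsis allows stopping 4 weeks after a confirmed complete response. If some of these subjects never progress, the rule understates the plateau that would be the most interesting feature of the data. The upper PFS percentiles, and the rates at selected weeks planned in Protocol 10.5.3.2 (not listed in SAP 9.5.2), depend on that part of the curve.

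For DOR, two programmers could each follow the SAP and report different quartiles. The dates differ whenever a non-PET assessment follows the last scan. Besides LTFU visits, Protocol 7.3.12.2 allows CT alone in dose escalation when PET is not feasible.

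**Working it through.** The documents give no PFS or DOR figure to reproduce.

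**Ten subjects, no model.** Four have events by week 25. Three stop treatment progression-free at week 35, have PET-CT at week 37 and are clear at every LTFU visit to week 101. Two have an end-of-treatment PET-CT at week 101. One progresses at week 59.

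- After week 25, PFS is 6/10 = 60%.
- SAP rule: the three are censored at week 37, so 3 are at risk at week 59; 60% × 2/3 = 40%.
- Last-assessment censoring: 6 are at risk; 60% × 5/6 = 50%.

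**Simulation with treatment ending at progression.** From the documents: scans at weeks 5, 15 and 25 and 2 weeks after the last dose; 6-weekly LTFU visits from 30 days after the last dose to week 104; median treatment about 8 months (35 weeks; Protocol 3.5.1). Assumed: exponential event times with median 26 weeks in progressors, a fraction c never progressing, 15% of events being deaths, and a constant rate of other-cause discontinuation. True PFS is c + (1 − c) × 0.5^(t/26). At week 100, 0.5^(100/26) = 0.0695, giving 0.20 + 0.80 × 0.0695 = 26% and 0.30 + 0.70 × 0.0695 = 35%.

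Week-100 PFS, N = 55, no PET-CT in LTFU (2000 replicates, Monte Carlo SE at most 0.2 points):

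| Treatment pattern | SAP rule, c = 20% / 30% | Last assessment | True |
|---|---|---|---|
| Stops only for progression (median 40 / 48 weeks) | 26% / 35% | 26% / 35% | 26% / 35% |
| Median 35 weeks | 24% / 30% | 26% / 35% | 26% / 35% |
| Median 24 weeks | 18% / 23% | 26% / 35% | 26% / 35% |
| Half of those event-free at week 25 stop at week 29 | 17% / 25% | 26% / 35% | 26% / 35% |

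Variations:

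- PET-CT at LTFU visits: 26% and 35%, no bias.
- LTFU for survival only, so that only late deaths are asymmetric: 25% and 32% at 35 weeks of treatment; 19–20% and 26–27% with shorter treatment or stops in response.
- Progressor median 40 weeks, 35 weeks of treatment: 26% against true 34%, and 32% against 42%. Progressor median 16 weeks: no gap.
- No never-progressors: both rules 8% (true 7%) when treatment stops only for progression; SAP rule 4% against 7% with stops in response.
- At 35 weeks of treatment, week-52 PFS is 41% and 47% under the SAP rule (true 40% and 47.5%); medians are 39 and 48 weeks (true 37 and 47).
- 75th percentile with c = 20%: 96 weeks at 35 weeks of treatment and 74–78 with shorter treatment or stops in response, against a true 104.
- N = 15: averages within 1 point of these, but the trial-to-trial SD is 11–14 points with 2–3 at risk at week 100.

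**Cross-check with a different model.** 40,000 subjects per scenario, no never-progressors, 30% of events deaths, time on treatment drawn independently of progression. With true median PFS of 12 months, week-78 PFS is 24.4% (true 35.4%; last assessment 36.2%) and the estimated median is 10.9 months. With true median 24 months, they are 43.6% (true 59.5%; last assessment 60.5%) and 16.2 months. With true median 3 months the effect is negligible (1.4% against 1.6%). The direction agrees. The gaps are larger because event-free subjects leave treatment sooner than when progression itself ends treatment.

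**DOR, 22 responders (40% of 55), 30% never progressing.** The two sentences give different medians in 12% of trials at 35 weeks of treatment and in 42–45% with shorter treatment or stops in response. At least one quartile differs in 33% and 73–76%. Duration beyond 78 weeks is estimated as 42% against 37%, and 42% against 31–32% (true 41%). With 6 responders at least one quartile differs in 19–40%. With no never-progressors the medians agree in at least 99%.

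**The case against.** The PFS bias needs LTFU visits that can declare progression without PET-CT, and the documents do not establish that. Disease assessments elsewhere in Protocol 7.2 include PET/CT, and Appendix D gives only PET/CT response criteria. If LTFU visits include PET-CT there is no bias. If follow-up is for survival only, or only PET-CT can declare progression and no extra scans are triggered, late deaths alone remain asymmetric. This stands, and it is why the conclusion is conditional. But the scan footnote names no LTFU time point, and Protocol 7.2.4 refers to Table 8, which covers screening and cycle 1, so the text does not settle the matter.

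The sizes rest on assumptions outside the documents. A 20–30% never-progressing fraction is generous beside the 19% complete response rate Protocol 2.4.1 cites for blinatumomab in NHL; several plausible settings show no gap; N = 55 is the planned expansion of a study that stopped early; and at N = 15 noise usually exceeds the bias. All of this stands. Week-100 PFS is not a planned output. The 75th percentile is, but its true value sits at the 2-year follow-up limit, so those figures are only indicative.

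The one subject still on treatment at the primary analysis (SAP 7.2) has no scheduled scan between week 25 and end of treatment. If progression-free and without an extra scan, that subject is censored near week 25. SAP Section 10 already defers this follow-up to the final analysis.

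None of this removes the asymmetry in the text or the DOR contradiction.

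**Conclusion.** The concern holds. The PFS rule applies different follow-up clocks to subjects with and without events. If LTFU visits can find progression without PET-CT, late PFS tends to be too low; the direction follows from the definitions and the schedule.

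The size depends on assumptions. In the model where progression ends treatment, the week-100 gap runs from none to about 12 points (35% − 23%). At 35 weeks of treatment the median and week-52 PFS barely move. That reassurance is itself model-dependent: in the cross-check the median falls by 12 − 10.9 = 1.1 months or 24 − 16.2 = 7.8 months.

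The DOR contradiction exists in the text whatever LTFU contains, though it changes results only when a non-PET assessment follows the last scan. These are secondary, descriptive endpoints, and SAP 9.5 already expects limited efficacy data. This should be corrected before the analysis is programmed, but it does not threaten the study's main conclusions.

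**What to change.** - Use one rule for PFS and DOR: censor event-free subjects at the last disease assessment of a kind that can declare progression under the event definition. Delete the closing PET-CT sentence in the SAP's DOR definition.
- Reconcile the LTFU descriptions (Protocol 3.1 and SAP 3.1 against Protocol 7.2.4 and the SAP's LTFU definition), and state whether LTFU disease assessments include PET-CT.
- State how deaths long after the last assessment are counted.
- Flag the subject still on treatment at the primary analysis and rely on the final analysis. Clinical tumor assessments follow the PET-CT schedule, so the new rule alone does not move that date.
- As a sensitivity analysis, report the symmetric version: progression only on PET-CT, censoring at the last PET-CT, and a stated rule for later deaths. In simulation it did as well as the main rule (26% and 34–35% at week 100).

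The cost is SAP wording, one derived date and an entry in SAP Section 10, because Protocol 10.5.3.2 carries the same PFS rule. Protocol 7.2.4 already requires disease status at the 6-weekly visits; confirm that those dates are in the database. The downside is that clinical assessments are less precise than PET-CT, and delayed detection can push estimates slightly high: at 35 weeks of treatment, week-52 PFS by 1–2 points and the median by 2–3 weeks.
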